- Grade 3: study intervention is generally suspended and the high-dose corticosteroids (prednisone 1 to 2 mg/kg/day or methylprednisolone 1 to 2 mg/kg/day) treatment should be initiated. Corticosteroids should be tapered over the course of at least 4 to 6 weeks. Some refractory cases may require infliximab or other immunosuppressive therapy.

- Grade 4: in general, permanent discontinuation of study intervention is recommended, with the exception of endocrinopathies that have been controlled by hormone replacement.

Permanent treatment discontinuation is required in case of immune-related Grade 4 rash/inflammatory dermatitis, nephritis, autoimmune hemolytic anemia, hemolytic uremic syndrome, aplastic anemia, immune thrombocytopenia, acquired thrombotic thrombocytopenic purpura, inflammatory arthritis, myositis, and polymyalgia-like syndrome.

For Grade 4 immune-related lymphopenia, permanent treatment discontinuation will be required, if lymphopenia is considered immune-related in nature, no clear alternative explanation exists for the event, and Grade 4 lymphopenia does not resolve within 14 days. Permanent treatment discontinuation is not required when the AE is manifest by a single laboratory value out of normal range without any clinical correlates. In this case, treatment should be held until the etiology is determined. If the event is not considered immune related and resolves to Grade ≤ 1 restarting treatment may be considered.

- For Grade 1 immune-related pneumonitis: continue treatment. If clinically indicated, monitor participants weekly or more frequently as needed with history, physical examination, and pulse oximetry. If symptoms appear and/or changes in the physical examination are noted, treat as Grade 2.
- For myositis: in case of management with rituximab, treatment should be discontinued.

For organ/system specific management guidelines, see the guideline tables in [Appendix 5](#).

Recommended guidance and management for specific irAEs are provided in the current NCCN guideline available at <http://www.nccn.org>.

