Grading	Management
All Grades	In cases of suspected SJS or any mucous membrane involvement, discontinue ICPI treatment and monitor closely for improvement, regardless of grade
G1: NA	For SCARs, there is no G1 category; if lower BSA is involved with bullae or erosions, there should remain a high concern that this reaction will progress to G3 or G4
G2: Morbilliform ("maculopapular") exanthem covering 10%-30% BSA with systemic symptoms, lymphadenopathy, or facial swelling	
Hold ICPI and monitor patients closely every 3 days with G2 irAEs for progression to involvement of greater BSA and/or mucous membrane involvement
 
Consider following patients closely using serial photography
 
Initiate therapy with topical emollients, oral antihistamines, and medium- to high-strength topical corticosteroids
 
Consider initiation of prednisone (or equivalent) 0.5-1 mg/kg tapered over at least 4 weeks

G3: Skin sloughing covering < 10% BSA with mucosal involvement associated signs (e.g., erythema, purpura, epidermal detachment, mucous membrane detachment)	
Hold ICPI therapy and consult with dermatology
 
Treat skin with topical emollients and other petrolatum emollients, oral antihistamines, and high-strength topical corticosteroids; dimethicone may also be offered as an alternative to petrolatum
 
Administer IV (methyl)prednisolone (or equivalent) 0.5-1 mg/kg and convert to oral corticosteroids on response, wean over at least 4 weeks
 
Admit to burn and/or consult wound services with attention to supportive care, including fluid and electrolyte balance, minimizing insensible water losses, and preventing infection
 
Given the immune mechanism of action of these medicines, use of immune suppression is warranted and should be offered
 
For mucous membrane involvement of SJS or TEN, appropriate consulting services should be offered to guide management in preventing sequelae from scarring (e.g., ophthalmology; ear, nose, and throat; urology; gynecology; etc., as appropriate)

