2.0 GI Toxicities	
2.1 Colitis	
Definition: A disorder characterized by inflammation of the colon Diagnostic work-up	

G2 Work-up of blood (CBC, comprehensive metabolic panel, TSH, ESR, CRP), stool (culture, Clostridium difficile, parasite, CMV or other viral etiology, ova and parasite) should be performed Consider testing for lactoferrin (for patient stratification to determine who needs more urgent endoscopy) and calprotectin (to follow-up on disease activity) Screening laboratories (HIV, hepatitis A and B, and blood quantiferon for TB) to prepare patients to start infliximab should be routinely done in patients at high risk for those infections and appropriately selected patients based on infectious disease expert's evaluation Imaging (e.g., CT scan of abdomen and pelvis and GI endoscopy with biopsy) should be considered as there is evidence showing that the presence of ulceration in the colon can predict a corticosteroid refractory course, which may require early infliximab Consider repeating endoscopy for patients who do not respond to immunosuppressive agents; repeating endoscopy for disease monitoring can be considered when clinically indicated and when planning to resume therapy
	

G3-4 All the work-up listed for G2 (blood, stool, imaging, and scope with biopsy) should be completed immediately Consider repeating endoscopy for patients who do not respond to immunosuppressive agents; repeating endoscopy for disease monitoring should only be considered when clinically indicated and when planning to resume ICPI
	
Grading (based on CTCAE for diarrhea, as most often used clinically)	Management
All patients	
Counsel all patients to be aware of and inform their health care provider immediately if they experience: Abdominal pain, nausea, cramping, blood or mucus in stool or changes in bowel habits, fever, abdominal distention, obstipation, constipation For G2 or higher, consider permanently discontinuing CTLA-4 agents and may restart PD-1, PD-L1 agents if patient can recover to G1 or less; concurrent immunosuppressant maintenance therapy should be considered only if clinically indicated in individual cases

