G4: Life-threatening consequences; urgent intervention indicated	
Permanently discontinue treatment
 
Should admit patient when clinically indicated; patients managed as outpatients should be very closely monitored
 
Administer 1-2 mg/kg/d methylprednisolone or equivalent until symptoms improve to G1, and then start taper over 4-6 weeks
 
Consider early infliximab 5-10 mg/kg if symptoms refractory to corticosteroid within 2-3 days Consider lower GI endoscopy if symptoms are refractory despite treatment or there is concern of new infections

Additional considerations
 
The use of vedolizumab (not approved in Japan) may be considered in patients refractory to infliximab and/or contraindicated to TNF-α blocker. The decision should be made on an individual basis from gastroenterology and oncology evaluation. This is based on case series showing promising results
 
Patients with hepatitis and irAE colitis are rare, and management should include permanently discontinuing ICPI and offering other immunosuppressant agents that work systemically for both conditions
 
Currently, enteritis alone as the cause of diarrhea is uncommon and requires small bowel biopsy as the evaluation tool. It may be managed similar as colitis, including corticosteroid and/or infliximab, etc.
	

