7.6 Encephalitis	

Definition: As for aseptic meningitis, need to exclude infectious causes, especially viral (i.e., HSV). Confusion, altered behavior, headaches, seizures, short-term memory loss, depressed level of consciousness, focal weakness, speech abnormality
	

Diagnostic work-up Neurologic consultation MRI of brain with or without contrast may reveal T2/fluid-attenuated inversion recovery changes typical of what is seen in autoimmune encephalopathies or limbic encephalitis or may be normal Lumbar puncture: check cell count and protein glucose and perform Gram stain, culture, PCR for HSV and other viral PCRs depending on suspicion, cytology, oligoclonal bands, autoimmune encephalopathy, and paraneoplastic panels. May see elevated WBC count with lymphocytic predominance and/or elevated protein EEG to evaluate for subclinical seizures Blood: metabolic, CBC, ESR, CRP, ANCA (if suspect vasculitic process), thyroid panel including TPO and thyroglobulin Rule out concurrent anemia/thrombocytopenia, which can present with severe headaches and confusion
	
Grading	Management

G1: Mild, no interference with function and symptoms not concerning to patient. Note: Any cranial nerve problem should be managed as moderate. G2: Moderate, some interference with ADL, symptoms concerning to patient (i.e., pain but no weakness or gait limitation) G3-4: Severe, limiting self-care and aids warranted
	
Hold ICPI and discuss resumption with patient only after taking into account the risks and benefits As above for aseptic meningitis suggest concurrent IV acyclovir until PCR results obtained and negative Trial of methylprednisolone 1-2 mg/kg If severe or progressing symptoms or oligoclonal bands present, consider pulse corticosteroids methylprednisolone 1 g IV daily for 3-5 days plus IVIG 2 g/kg over 5 days If positive for autoimmune encephalopathy antibody and limited or no improvement, consider rituximab or plasmapheresis in consultation with neurology.

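### Appendix 5 gives conflicting study-drug instructions for Grade 4 colitis and for Grade 3 severe cutaneous adverse reactions (SCARs), so whether the drug may be resumed is left open

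*Protocol*

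**What the plan says.** **Colitis (Appendix 5, Table A2, 2.1).** The row for all patients states: "For G2 or higher, consider permanently discontinuing CTLA-4 agents and may restart PD-1, PD-L1 agents if patient can recover to G1 or less". The Grade 3 row repeats this in nearly the same words. The Grade 4 row states: "Permanently discontinue treatment".

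**SCARs (Appendix 5, Table A1, 1.3).** The row for all grades begins: "In cases of suspected SJS or any mucous membrane involvement, discontinue". It goes on to ask for close monitoring for improvement, and it applies at every grade. The Grade 3 definition begins: "G3: Skin sloughing covering < 10% BSA with mucosal involvement associated signs". The Grade 3 management cell says to hold the drug and consult dermatology. The Grade 4 cell requires permanent discontinuation.

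**Encephalitis and aseptic meningitis (Appendix 5, Table A7, 7.5 and 7.6).** One management cell covers Grades 1 to 4 for each event: hold, then "discuss resumption with patient only after taking into account the risks and benefits".

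**General rules.** Section 6.9.2 states: "Grade 4: in general, permanent discontinuation of study intervention is recommended, with the exception of endocrinopathies that have been controlled by hormone replacement". It then lists Grade 4 events for which permanent discontinuation is required, adds a separate rule for Grade 4 lymphopenia, and refers to Appendix 5 for organ-specific guidance. The Appendix 5 preface makes permanent discontinuation the Grade 4 default except where the tables say otherwise. The Grade 4 rule in Section 6.8 covers only treatment-related events that Appendix 5 does not address.

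**The concern.** A table of toxicity management works only if an event of a given grade leads to one instruction. Here an investigator with a Grade 4 colitis that has recovered to Grade 1 finds one row that permits restart and another that rules it out. An investigator with a Grade 3 SCAR meets one row that says discontinue and another that says hold.

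Two things follow. The first is patient safety: the row a site follows can decide whether a participant is exposed again after a serious immune-related event. Colitis is listed in Sections 2.3 and 6.9.2 among the important identified risks. Section 7.1.2.1 also allows one reinitiation course after discontinuation for an adverse event that has resolved or is well managed, and does not say whether an event labelled *permanent discontinuation* is excluded.

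The second is the safety summary. SAP 15.1 and 15.1.2 count temporary interruption (drug interrupted) and permanent discontinuation (drug withdrawn) as separate categories, and the restricted analysis in SAP 6.1 keeps both. The same event at the same grade could be counted in different tables depending on the site.

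**Working it through.** There is no planned figure to reproduce. The check sets the rows side by side for each event and grade.

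| Event and grade | General row in the same table | Grade-specific row | Agree? |
|---|---|---|---|
| Colitis, Grade 3 | PD-L1 agent may restart on recovery to Grade 1 or less | Same | Yes |
| Colitis, Grade 4 | PD-L1 agent may restart on recovery (Grade 4 lies within Grade 2 or higher) | Permanently discontinue | **No** |
| SCARs, Grade 3 | Discontinue for any mucous membrane involvement | Hold; mucosal involvement is part of the definition | **Unclear; depends on *discontinue*** |
| SCARs, Grade 4 | Discontinue | Permanently discontinue | Compatible |
| Encephalitis, aseptic meningitis, Grades 1 to 4 | None | Hold and discuss resumption | One instruction only |

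**Colitis Grade 4: does another passage settle it?**
- Bintrafusp alfa contains an anti-PD-L1 antibody (Section 2), so the restart clause reaches it.
- The Appendix 5 preface defers to the tables, and this table disagrees with itself.
- Colitis is not among the named Grade 4 events in the preface or in Section 6.9.2.
- The Grade 4 rule in Section 6.8 excludes events covered by Appendix 5.
- The work-up cell for Grades 3 and 4 mentions endoscopy when resumption is planned, so resumption is contemplated at a level that includes Grade 4.

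No other passage states which row prevails.

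**SCARs Grade 3: what does *discontinue* mean?**
- Table A8, 8.4 (aplastic anemia, Grade 3) uses it for a stop that ends when the event returns to Grade 1.
- Table A7, 7.2 (Guillain-Barré syndrome) uses plain *discontinue* at Grade 2 and *permanently discontinue* at Grades 3 and 4, so the two appear to differ.
- Section 6.8 speaks of discontinuation that may be permanent or transient.

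If the word means a temporary stop, the two SCARs rows are nearly equivalent. If it means a lasting stop, they conflict for every Grade 3 case, because every such case has mucosal involvement by definition. The protocol does not say which.

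**How likely is a case?** The documents give no rate for either event, so the true rate p is an assumption. With n = 135 (Section 4.1), the chance of at least one case is 1 − (1 − p)^135:
- p = 0.1%: 1 − 0.999^135 = 0.13
- p = 0.5%: 1 − 0.995^135 = 0.49
- p = 1%: 1 − 0.99^135 = 0.74

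**The case against.** The case for leaving the text alone has several parts.

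*The colitis rows can be read together.* The row for all patients is general counselling, speaks partly of CTLA-4 agents not used here, and is permissive. The Grade 4 row is specific and directive, and in line with the general Grade 4 recommendation. Many readers would let the specific row govern. That is a reasonable way to read, but the protocol does not state it, and the general row names Grade 2 or higher without an upper limit.

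*SCARs may be only a matter of terms.* The row for all grades omits *permanently* and asks for monitoring for improvement, and the Grade 3 row does not itself offer resumption. This stands: the SCARs conflict is no stronger than the undefined word. The gap remains, because a site cannot tell whether resumption is open.

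*Sites would not act in opposite ways at onset.* This also stands. For both events the drug is held or stopped at first; the difference is in later restart. Section 6.8 calls for Medical Monitor consultation when two or more doses are missed for an adverse event, and Section 7.1.2.1 requires the Medical Responsible's agreement to reinitiation. These safeguards limit unilateral restart but do not supply the missing rule.

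A reader might also infer that encephalitis and aseptic meningitis are a third contradiction, because Table A7 allows resumption at Grade 4 while Section 6.9.2 recommends permanent discontinuation. The documents do not support that. Appendix 5 gives one instruction for each event. Section 6.9.2 speaks only in general terms, points to the tables, and leaves both events off its required list; its lymphopenia rule shows that controlled endocrinopathies are not the sole departure. The preface lets the tables differ from the default. A cross-reference would help, but this is a clarification only.

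**Conclusion.** The point holds for two events, each at one grade. Grade 4 colitis carries two incompatible instructions on restart. Grade 3 SCARs carry two instructions whose compatibility depends on an undefined term. Both pairs of passages must be reconciled.

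A reader might extend the finding to Grades 3 and 4 of both events. That is too broad: the colitis Grade 3 row matches the row for all patients, and the SCARs Grade 4 row is compatible with the row for all grades.

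By definition the overlap reaches every Grade 3 SCAR and every Grade 4 colitis that recovers to Grade 1 or less. The number of cases is unknown: the 13% to 74% range rests on assumed rates of 0.1% to 1% for one event, which the documents neither support nor exclude, and for colitis it counts cases before any recovery. The effect on the interruption and withdrawal tables is possible but cannot be sized. The primary endpoint analysis and the sample size are not in question.

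**What to change.** - In Table A2, 2.1, reconcile the row for all patients with the Grade 4 row, so that Grade 4 colitis carries one instruction on restart.
- In Table A1, 1.3, reconcile the row for all grades with the Grade 3 row.
- Define *hold*, *discontinue* and *permanently discontinue* once, use them consistently through Appendix 5, and state how each relates to reinitiation under Section 7.1.2.1.
- As a minor clarification, cross-reference the encephalitis and aseptic meningitis cells in Table A7 with the Grade 4 sentence in Section 6.9.2 and the preface.

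Which rule applies is for the sponsor's medical team to decide. The cost is a clarification letter to sites, or a table correction in the next amendment, with no change to sample size or data collection.

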2.0 GI Toxicities	
2.1 Colitis	
Definition: A disorder characterized by inflammation of the colon Diagnostic work-up	

G2 Work-up of blood (CBC, comprehensive metabolic panel, TSH, ESR, CRP), stool (culture, Clostridium difficile, parasite, CMV or other viral etiology, ova and parasite) should be performed Consider testing for lactoferrin (for patient stratification to determine who needs more urgent endoscopy) and calprotectin (to follow-up on disease activity) Screening laboratories (HIV, hepatitis A and B, and blood quantiferon for TB) to prepare patients to start infliximab should be routinely done in patients at high risk for those infections and appropriately selected patients based on infectious disease expert's evaluation Imaging (e.g., CT scan of abdomen and pelvis and GI endoscopy with biopsy) should be considered as there is evidence showing that the presence of ulceration in the colon can predict a corticosteroid refractory course, which may require early infliximab Consider repeating endoscopy for patients who do not respond to immunosuppressive agents; repeating endoscopy for disease monitoring can be considered when clinically indicated and when planning to resume therapy
	

G3-4 All the work-up listed for G2 (blood, stool, imaging, and scope with biopsy) should be completed immediately Consider repeating endoscopy for patients who do not respond to immunosuppressive agents; repeating endoscopy for disease monitoring should only be considered when clinically indicated and when planning to resume ICPI
	
Grading (based on CTCAE for diarrhea, as most often used clinically)	Management
All patients	
Counsel all patients to be aware of and inform their health care provider immediately if they experience: Abdominal pain, nausea, cramping, blood or mucus in stool or changes in bowel habits, fever, abdominal distention, obstipation, constipation For G2 or higher, consider permanently discontinuing CTLA-4 agents and may restart PD-1, PD-L1 agents if patient can recover to G1 or less; concurrent immunosuppressant maintenance therapy should be considered only if clinically indicated in individual cases

G1: Increase of fewer than four stools per day over baseline; mild increase in ostomy output compared with baseline	
Continue ICPI; alternatively, ICPI may be held temporarily and resumed if toxicity does not exceed G1 Monitor for dehydration and recommend dietary changes Facilitate expedited phone contact with patient/caregiver May obtain gastroenterology consult for prolonged G1 cases

G2: Increase of four to six stools per day over baseline; moderate increase in ostomy output compared with baseline	
Should hold ICPI temporarily until patient's symptoms recover to G1; can consider permanently discontinuing CTLA-4 agents and may restart PD-1, PD-L1 agents if patient can recover to G1 or less Concurrent immunosuppressant maintenance therapy (10 mg prednisone equivalent dose) may be offered only if clinically indicated in individual cases May also include supportive care with medications such as Imodium if infection has been ruled out Should consult with gastroenterology for G2 or higher

2.0 GI Toxicities	
	
Administer corticosteroids, unless diarrhea is transient, starting with initial dose of 1 mg/kg/day prednisone or equivalent
 
When symptoms improve to G1 or less, taper corticosteroids over at least 4-6 weeks before resuming treatment, although resuming treatment while on low-dose corticosteroid may also be an option after an evaluation of the risks and benefits
 
EGD/colonoscopy, endoscopy evaluation should be highly recommended for cases Grade ≥ 2 to stratify patients for early treatment with infliximab based on the endoscopic findings and to determine the safety of resuming PD-1, PD-L1 therapy
 
Stool inflammatory markers can be considered (lactoferrin and calprotectin) in cases of G2 or higher to differentiate functional versus inflammatory diarrhea, and use calprotectin to monitor treatment response if provider prefers
 
Repeat colonoscopy is optional for cases of G2 or higher for disease activity monitoring to achieve complete remission, especially if there is a plan to resume ICPI

G3: Increase of seven or more stools per day over baseline, incontinence, hospitalization indicated, severe increase in ostomy output compared with baseline, limiting self-care ADL	
Should consider permanently discontinuing CTLA-4 agents and may restart PD-1, PD-L1 agents if patient can recover to G1 or less.
 
Administer corticosteroids (initial dose of 1-2 mg/kg/d prednisone or equivalent)
 
Consider hospitalization or outpatient facility for patients with dehydration or electrolyte imbalance
 
If symptoms persist ≥ 3-5 days or recur after improvement, consider administering IV corticosteroid or noncorticosteroid (e.g., infliximab)
 
Consider colonoscopy in cases where patients have been on immunosuppression and may be at risk for opportunistic infections as an independent cause for diarrhea (i.e., CMV colitis) and for those who are anti-TNF or corticosteroid refractory

G4: Life-threatening consequences; urgent intervention indicated	
Permanently discontinue treatment
 
Should admit patient when clinically indicated; patients managed as outpatients should be very closely monitored
 
Administer 1-2 mg/kg/d methylprednisolone or equivalent until symptoms improve to G1, and then start taper over 4-6 weeks
 
Consider early infliximab 5-10 mg/kg if symptoms refractory to corticosteroid within 2-3 days Consider lower GI endoscopy if symptoms are refractory despite treatment or there is concern of new infections

Additional considerations
 
The use of vedolizumab (not approved in Japan) may be considered in patients refractory to infliximab and/or contraindicated to TNF-α blocker. The decision should be made on an individual basis from gastroenterology and oncology evaluation. This is based on case series showing promising results
 
Patients with hepatitis and irAE colitis are rare, and management should include permanently discontinuing ICPI and offering other immunosuppressant agents that work systemically for both conditions
 
Currently, enteritis alone as the cause of diarrhea is uncommon and requires small bowel biopsy as the evaluation tool. It may be managed similar as colitis, including corticosteroid and/or infliximab, etc.
	

